**I. PURPOSE OF THE STUDY AND BACKGROUND**

**Ia. Background and Significance**

Ultrasound is now widely accepted as a diagnostic tool for use in the emergency department, as supported by the American College of Emergency Physicians (ACEP) position statement in 2001 (revised in 2008). In addition, the American Academy of Pediatrics (AAP) policy statement in 2015 (also supported by The Society for Academic Emergency Medicine (SAEM), ACEP, and World International Network Focused on Critical Ultrasound (WINFOCUS)) now requires point-of-care ultrasound education for PEM fellowship training. Ultrasound is particularly useful in pediatrics as it is rapid, reliable, portable, easy to use, does not require the patient to remain motionless and does not use ionizing radiation.

Ultrasound has been shown to have applications in the evaluation and diagnosis of pediatric skeletal injuries. There are a number of studies in the literature that support the use of ultrasound in fracture diagnosis. Grechenig et al studied the ability of ultrasound to pick up fractures in cadavers with the goal of delineating the minimum fracture size that could be detected on ultrasound. With the use of high resolution ultrasonography (7.5MHz), cortical discontinuities greater than or equal to 1 mm were identified on all study subjects. Fractures were studied in both longitudinal and cross-sectional views as the authors noted that fractures

 American College of Emergency Physicians Policy Statement. Emergency Ultrasound Guidelines. Ann Emerg Med. April 2009;53(4):550-70.

 Grechenig et al. Scope and limitations of ultrasonography in the documentation of fractures—an experimental study. Arch Orthop Traum Surg 1998; 117(6-7): 368-71.

IRB #:

Version 1.2

could potentially escape detection if the transducer is placed parallel to the course of the fracture. Fractures were demonstrated as either cortical discontinuities or interruptions in acoustic shadows.

Several studies in the pediatric literature have shown that ultrasound can adequately identify long bone fractures, determine the need for reduction of a displaced fracture and assess the adequacy of reduction when compared to plain films. In a prospective study involving pediatric emergency medicine (PEM) physicians by Patel et al, ultrasound was compared to plain films to identify fractures, determine need for reduction and assess adequacy of reduction. The study found a 95.5% agreement between ultrasound and radiography in fracture identification, a 92.3% agreement in need for fracture reduction and a 92.3% agreement in adequacy of reduction.

In a case study, Durston and Swartzentruber described three cases in which ultrasound was helpful in guiding fracture reduction. Chen et al, in a prospective study, compared ultrasound to x-ray for the diagnosis of forearm fractures and used ultrasound as a real-time imaging modality to guide the reduction procedure. They found 97% sensitivity and 100% specificity in the diagnosis of forearm fractures with ultrasound compared to plain films and the initial success rate of ultrasound-guided reduction was 92% with two patients requiring repeat reduction. Two of 65 fractures were missed, both ulnar styloid fractures in patients who also had radial metaphysis fractures and therefore the management was not altered because of the missed diagnosis. However, this study did not compare ultrasound-guided reduction to blinded reduction or reduction with another mode of real-time imaging such as fluoroscopy.

Of note, children tolerate musculoskeletal ultrasound, even in areas of injury, very well. Chien, et al. evaluated the use of ultrasound for the diagnosis of clavicular fractures in children and found that the ultrasound examination was not associated with an increase in pain. While not formally studied, both Patel et al and Chen et al noted that with liberal application of ultrasound transmission gel, there was no worsening of pain and patients did not require additional pain medication during the ultrasound exam^7.

One pediatric study, by Dubrovsky et al, compared the use of ultrasound guided reduction to reduction with fluoroscopy to accurately determine successful fracture realignment. Study physicians used ultrasound to assess the fracture prior to and after reduction, with the option of dynamic visualization during reduction. Fluoroscopic images were obtained after ultrasound images. When comparing the treating physician's interpretation of ultrasound results to a blinded orthopedic surgeon's interpretation of the fluoroscopy results, with a positive test indicating an inadequately reduced fracture, the sensitivity was 50%, specificity 89%, negative

---

Patel et al, The Utility of bedside ultrasonography in identifying fractures and guiding fracture reduction in children, *Pediatric Emergency Care*, 2009 April; 25(4): 221-2

Durston, Swartzentruber, Ultrasound guided reduction of pediatric forearm fractures in the ED, *Am J Emerg Med* 2000 Jan, 18(1): 72-77

Chen et al, Diagnosis and guided reduction of forearm fracture in children using bedside ultrasound, *Peds Emerg Care*, 2007 Aug; 23(8) 528-531

Chien M et al, Bedside ultrasound in the diagnosis of pediatric clavicle fractures, *Pediatr Emerg Care* 2011 Nov 27(11); 1038-41

Dubrovsky et al, Accuracy of ultrasonography for determining successful realignment of pediatric forearm fractures, *Annals of Emergency Medicine*, *Ann Emerg Med* 2015 Mar; 65(3): 260-5

IRB #:

Version 1.2

predictive value was 95.3% and positive predictive value was 28.6%, indicating that ultrasound was best at identifying adequately aligned fractures. Additionally, 78% of physicians indicated that ultrasound was helpful with the reduction procedure.

The use of ultrasound for real-time guidance of fracture reduction compared to blind reduction has been assessed in the adult literature. In a before-and-after study, Ang et al, compared ultrasound guided reduction to a retrospective control group who underwent blinded fracture reduction and showed a decreased rate in the number of repeat reductions. In a similar before-and-after study, Chinnock et al, showed no significant difference in successful reduction rates with ultrasound compared to blinded reduction. Brahm J et al, in an unpublished abstract, conducted a randomized, single blinded study of adult patients comparing ultrasound guided reduction to standard closed reduction of distal radius fractures and found no difference in the adequacy of reduction, time to reduction or number of repeat reductions between the groups.

It is apparent from these studies that there is a role for ultrasound in guiding fracture reduction. Using ultrasound for dynamic visualization instead of fluoroscopy has several advantages. Ultrasound provides no ionizing radiation, while fluoroscopy exposes the patient, caretaker, and provider to ionizing radiation, requiring shielding for all involved to minimize exposure. Fluoroscopy requires the use of a large, cumbersome machine and many emergency departments, including our institution, are not equipped with fluoroscopic equipment. We intend to build on the studies of Chen et al, Patel et al, and others, with a randomized controlled trial to compare the use of real-time ultrasound guidance of closed forearm fracture reduction to blinded closed forearm fracture reduction in the pediatric emergency department.

## **Ib. Objectives/Purpose of the study**

Our objective is to conduct a prospective randomized trial to assess the utility of using real-time ultrasound imaging in the reduction of forearm fractures in the PED. We also plan to assess provider satisfaction with using ultrasound for the reduction procedure compared to fracture reduction without use of ultrasound. We hypothesize that the use of ultrasound will improve patient outcomes and provider satisfaction. Thus, the primary outcome of the study will be:

- 1) To compare the number of patients requiring a repeat reduction procedure between the experimental group (ultrasound guided fracture reduction) and control group (standard of care forearm fracture reduction).

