### **Secondary Outcomes:**

- 1) To compare provider satisfaction with the reduction procedure between the two groups. Specifically, we will ask providers to determine:
  - I. Providers from experimental group:
    - a. Ease of fracture reduction - scale 1-5, (1=easy 5=very difficult)

---

Ang et al, Ultrasound-guided reduction of distal radius fractures, Am J of Emerg Med, 2010; 28, 1002-1008

Chinnock et al, Ultrasound-guided reduction of distal radius fractures, J of Emerg Med, 2011, 40 (3) 308-312

 Brahm J et al, A Randomized controlled trial of emergency department ultrasound-guided reduction of distal radius fractures, Annals of Emerg Med-Abstracts, 2011 Oct; 58(4), 230

IRB #:

Version 1.2

- b. Ease of using ultrasonography on a 5 point scale (1=easy, 5=very difficult).
- c. Was ultrasound helpful in completing the fracture reduction? a) yes b) no c) uncertain

II. Providers from control group:

- a. Ease of fracture reduction - scale 1-5, (1=easy 5=Most difficult)
- b. Do you think real-time imaging would have been helpful for this reduction?

|

- 2) To compare the adequacy of reduction between groups by measuring and comparing the degree of angulation and displacement on the post reduction x-rays. An orthopedic surgeon who is blinded to the patient's group assignment will read the x-rays. The acceptable degree of angulation will be the same in both groups. The acceptable degree of angulation based on age is less than 20 degrees' angulation for patients younger than 10 years of age and less than 10 degrees' angulation for patients older than 10 years of age.
- 3) To compare the time for the fracture reduction procedure between the experimental and control group.
- 4) To compare the number of patients requiring operative repair after reduction between the experimental and control group.
- 5) To compare the post-reduction ultrasound and x-ray interpretation, including measurement of degree of angulation and displacement on the ultrasound and x-ray for each patient.

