#### **IIId. Number of Subjects**

From a retrospective chart review sampling of displaced forearm fractures requiring reduction from June 1 to August 31, 2015 at CHAM, there were 20 displaced forearm fractures that underwent a closed reduction procedure in the Pediatric Emergency Department. 5 of the 20 displaced forearm fractures (25%) were inadequately reduced and required repeat reduction and/or operative management. Based on a recent study by Wellsh et al, only 6% of patients required repeat fracture reduction when US guidance was used.

In order to observe such a difference with 80% power, the sample size calculation would require a minimum of 56 patients in each group (standard of care vs US-guided reduction) with alpha set at P= 0.05.

Statistical significance will be assessed using mean, percentages, frequency distributions, and p-value. The significance will be set at 0.05. The test statistic used will be the Chi-square test. Confidence intervals will also be obtained. After the primary analysis of the group differences, logistic or normal regression will be used to determine factors related to these outcomes. The significance will be set at 0.05. The statistical approaches will be further developed with the assistance of the statistician in the orthopaedic surgery department following data collection and study approval.

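### The primary outcome counts repeat reductions only, so a failed first reduction that goes straight to operation is a non-event, although the sample size counts operation as failure

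*Combined protocol and SAP*

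**What the plan says.** Section Ib states the primary outcome as "To compare the number of patients requiring a repeat reduction procedure between the experimental group" and the control group. It does not mention operation and does not define a repeat reduction. Item 4 of the Secondary Outcomes is a separate count: "To compare the number of patients requiring operative repair after reduction between the experimental and control group".

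The Number of Subjects section uses a wider event for the control arm: "5 of the 20 displaced forearm fractures (25%) were inadequately reduced and required repeat reduction and/or operative management". For the ultrasound arm it uses a narrower one: "only 6% of patients required repeat fracture reduction when US guidance was used". From these two rates it derives "a minimum of 56 patients in each group" and names the chi-square test.

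Section IIIa says that after the post-reduction x-ray the orthopedic surgeon decides whether a repeat reduction is needed. It gives no rule for recording a patient who goes to operation instead. Section Ic limits blinding to the surgeon who reads the x-rays and measures angulation and displacement. No blinding is stated for the decision on what follows the first reduction.

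Section IIIb names a different primary endpoint: the percentage of patients with adequate angulation on the post-reduction x-ray.

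**The concern.** After an inadequate first reduction a patient may have a second closed reduction, an operation, or both. The section Ib outcome registers only the first and third of these. A patient who goes directly to operation has no repeat reduction and, read literally, falls in the no-event cell of the 2×2 table beside patients whose first reduction was satisfactory.

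This would be harmless to the comparison only if direct operation were rare or equally common in both arms. If the arms differ, repeat-reduction rates can differ while first-attempt failure is identical. The trial could then report fewer repeat reductions with one technique when the technique had not made reductions more successful. The reverse is equally possible: a real benefit could be hidden.

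The endpoint also fails to match its own planning rate. The 25% includes failures managed by operation; the outcome to which it is applied does not.

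**Working it through.** **1. The plan's own figure.** Inputs from Number of Subjects: p1 = 0.25, p2 = 0.06, power 80%, alpha 0.05 (taken as two-sided; the section does not say). With the pooled-variance formula and p̄ = (0.25 + 0.06)/2 = 0.155:

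n = [1.960·√(2·p̄(1−p̄)) + 0.842·√(p1(1−p1) + p2(1−p2))]² / (p1−p2)²
= (1.003 + 0.416)² / 0.19² = 2.013 / 0.0361 = 55.8, so 56 per group.

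The stated figure reproduces. Power at 56 is 80.2%. It depends on using the wider event for control and the narrower event for ultrasound.

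**2. Effect of diversion on the primary comparison.** Let first-attempt failure be 25% in both arms, so there is no true difference in failure. Let d be the share of failures that go straight to operation. The observed repeat-reduction rate is 0.25 × (1 − d). The values of d are assumptions, since the documents give none. The rejection probability is by exact enumeration of two binomials with n = 56 each, chi-square without continuity correction, at 0.05.

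| d, control vs ultrasound | Repeat rates | Probability of p ≤ 0.05 |
|---|---|---|
| 0% vs 0% | 25% vs 25% | 5.1% |
| 10% vs 10% | 22.5% vs 22.5% | 5.1% |
| 10% vs 20% | 22.5% vs 20% | 6.4% |
| 10% vs 30% | 22.5% vs 17.5% | 10.3% |
| 10% vs 40% | 22.5% vs 15% | 17.7% |
| 0% vs 50% | 25% vs 12.5% | 40.4% |

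With a continuity correction the last two rows become 11.6% and 30.5%. The plan does not say which form of the test it will use. Equal diversion leaves the error rate at its nominal level; the problem comes from unequal diversion.

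**3. Power with both rates on the wider definition.** Control stays at 25%. Ultrasound becomes 6% + q, where q is the percentage of ultrasound patients who go straight to operation (not given, so assumed). For q = 2 points, p2 = 0.08 and p̄ = 0.165:

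z = (0.17·√56 − 1.960·√(2·0.165·0.835)) / √(0.25·0.75 + 0.08·0.92) = (1.272 − 1.029)/0.511 = 0.476, giving power 68.3%.

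| q (points) | Ultrasound rate | n per group for 80% | Power at 56 |
|---|---|---|---|
| 0 | 6% | 56 | 80.2% |
| 1 | 7% | 64 | 74.5% |
| 2 | 8% | 74 | 68.3% |
| 4 | 10% | 100 | 55.2% |

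**4. Power with both rates on the narrow definition.** If section Ib is left alone and k of the 5 chart-review failures had operation only (k not given), the control rate is (5 − k)/20. With ultrasound held at 6%: k = 1 gives 20%, 90 per group and 59.8% power at 56; k = 2 gives 15%, 181 per group and 34.1%. The mismatch therefore matters whichever definition is kept, unless k and q are both zero.

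**The case against.** The strongest objection is that section Ib leaves the coding unsettled. Because the planning rate includes operation, the authors may have meant operation to count. That is possible, but nothing says so, and listing operation as a separate secondary outcome points the other way. The literal reading stands until the text is changed.

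Second, the data are not lost. Operation is compared by arm under secondary outcome 4, and adequacy of reduction is read on x-ray by a blinded surgeon under secondary outcome 2. A shift from repeat reduction to operation would tend to show there. This stands as mitigation, but a secondary count does not correct the primary test.

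Third, under the section IIIb endpoint a patient operated on for angulation outside the limits would already be a failure. This also stands: the point applies to the section Ib definition, and the two statements have to be reconciled in any case.

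Fourth, repeat reduction alone keeps comparability with earlier studies and with the source of the 6%. Showing the components separately preserves that.

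A reader might go further and infer that the endpoint scores the worst failures as successes, or that repeated scanning leads surgeons to skip a second closed attempt in the ultrasound arm. The documents support neither. They do not rank operation against repeat reduction, and they say nothing about how scanning affects the next step. Nor do they show that any of the 5 chart-review failures had operation alone; the wording only allows it.

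**Conclusion.** The point holds for the section Ib primary outcome. As written, direct operation after an inadequate first reduction is a non-event, while the sample-size section treats the same course as failure. Since no blinding is stated for the decision that follows the first reduction, nothing in the design ensures that such cases are balanced between arms.

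The size is unknown. Under equal 25% failure and 56 per arm, the chance of a significant primary result runs from 5.1% (no or equal diversion) through 6.4% and 10.3% for moderate imbalance to 17.7% and 40.4% for large imbalance. Those shares are assumptions, and all the unequal ones were set in favour of ultrasound; the documents fix neither amount nor direction. The upper figures should not be read as the trial's expected error rate.

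The inconsistency between the planning rates rests on the text alone. The 80% power is reached only if the 6% would be unchanged on the wider definition, or if none of the 5 control failures had operation alone and the narrow definition is kept. The change should be made before data are analysed.

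**What to change.** In section Ib, define the primary event as a repeat reduction or operative management for an inadequate first reduction, whichever comes first, within a stated follow-up window. State how operation for inadequate reduction is to be identified. Report the two components by arm, and keep operative repair as secondary outcome 4.

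Reconcile this with section IIIb, so that one primary endpoint is named throughout.

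In Number of Subjects, restate both planning rates on the chosen definition, give the split of the 5 chart-review failures, and redo the power. If 2 further points of the ultrasound arm go straight to operation, power at 56 per group is about 68%, and 74 per group would be needed for 80%.

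Cost: both components are already trial outcomes, so this adds no new type of outcome beyond the window and the rule for identifying the event, and no treatment decision changes. The event becomes slightly broader than repeat reduction, and the stated power is likely to be less favourable.

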### **Secondary Outcomes:**

- 1) To compare provider satisfaction with the reduction procedure between the two groups. Specifically, we will ask providers to determine:
  - I. Providers from experimental group:
    - a. Ease of fracture reduction - scale 1-5, (1=easy 5=very difficult)

---

Ang et al, Ultrasound-guided reduction of distal radius fractures, Am J of Emerg Med, 2010; 28, 1002-1008

Chinnock et al, Ultrasound-guided reduction of distal radius fractures, J of Emerg Med, 2011, 40 (3) 308-312

 Brahm J et al, A Randomized controlled trial of emergency department ultrasound-guided reduction of distal radius fractures, Annals of Emerg Med-Abstracts, 2011 Oct; 58(4), 230

IRB #:

Version 1.2

- b. Ease of using ultrasonography on a 5 point scale (1=easy, 5=very difficult).
- c. Was ultrasound helpful in completing the fracture reduction? a) yes b) no c) uncertain

II. Providers from control group:

- a. Ease of fracture reduction - scale 1-5, (1=easy 5=Most difficult)
- b. Do you think real-time imaging would have been helpful for this reduction?

|

- 2) To compare the adequacy of reduction between groups by measuring and comparing the degree of angulation and displacement on the post reduction x-rays. An orthopedic surgeon who is blinded to the patient's group assignment will read the x-rays. The acceptable degree of angulation will be the same in both groups. The acceptable degree of angulation based on age is less than 20 degrees' angulation for patients younger than 10 years of age and less than 10 degrees' angulation for patients older than 10 years of age.
- 3) To compare the time for the fracture reduction procedure between the experimental and control group.
- 4) To compare the number of patients requiring operative repair after reduction between the experimental and control group.
- 5) To compare the post-reduction ultrasound and x-ray interpretation, including measurement of degree of angulation and displacement on the ultrasound and x-ray for each patient.

#### | **Ic. Study Design**

The study will be a prospective randomized, controlled, single blinded study. The study is single blinded in that the orthopedic surgeon reading the x-rays and determining the degree of angulation and displacement will be blinded to all patient characteristics and the patient's group assignment.

## **II. CHARACTERISTICS OF THE RESEARCH POPULATION**

#### **IIa. Inclusion Criteria**

Patients from 0- 21 years of age, male or female, who present to the Pediatric Emergency Department (PED) with a confirmed displaced forearm fracture that will require reduction by orthopedic surgery in the PED will be eligible for inclusion in this study.

#### **IIb. Exclusion criteria**

- 1) Patients with open fractures.
- 2) Patients with neurovascular compromise.
- 3) Unstable patients with life-threatening injuries who require ongoing resuscitation.

#### **IIc. Vulnerable subjects:**

The population of interest in this study includes patients < 18 years old (i.e. vulnerable subjects). All efforts will be made to protect these children during this study. As mentioned before, ultrasound emits no radiation and is a painless procedure; therefore, this study presents

---

Daruwalla, JS, 1979; Textbook: Rockwood and Wilkins' Fractures in Children

IRB #:

Version 1.2

no risk to these patients. If the patient expresses any discomfort from the ultrasound examination, the procedure will be immediately discontinued and the patient will be removed from the study. The purpose of investigating ultrasound guidance for fracture reduction in this vulnerable population was mentioned in the background section.

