Consulting orthopedic residents will be trained to perform musculoskeletal sonography for this study (see below for standardized training of study physicians in ultrasound) and will be considered study-trained physicians. All patients will undergo procedural sedation and/or pain management for closed reduction as per standard of care in the PED. The medication used for sedation and/or pain will be determined by the treating PEM physician. Study patients that are randomized to the ultrasound guided group will undergo a point-of-care ultrasound, performed by a study trained physician using a Sonosite Edge ultrasound machine with an L38 linear 10-5 MHz transducer probe.

Prior to the reduction procedure in patients randomized to the experimental group, ultrasound images of the fracture site will be obtained and the maximum degree of displacement will be measured. The ultrasound technique involves placing ultrasound gel over the fracture site and then placing the ultrasound probe in contact with the gel but not with the underlying skin. Both longitudinal and transverse views of the injured area will be obtained. Fractures are identified as an irregularity or interruption of the cortex of the bone. The degree of displacement is measured by drawing two intersecting lines along the edge of the cortex at the fracture site, generating an angle. Displacement measurements are then made by calculating the distance from the normal cortex to the fractured edge of the cortex.

The trained physician will then perform real-time ultrasound imaging as needed during the closed reduction procedure. Real-time ultrasound imaging includes both longitudinal and transverse views of the fracture site, repeated as often as necessary until the best alignment can be obtained. Once the orthopedic resident determines that he/she has obtained optimal alignment and prior to casting, a post-reduction ultrasound image will be obtained and the angle of displacement will again be measured. All ultrasounds performed prior to and after the reduction will be recorded, and the images obtained will include video clips of the ultrasound as well as a saved still picture of the best image of the suspected fracture site. The study-trained physician who performed the ultrasound will then record his/her findings on the data collection form immediately after the procedure and prior to reviewing plain radiographs.

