While it has been our experience that the majority of reduction procedures performed in the PED are done without the use of any real time imaging, some orthopedic surgery residents employ the use of the c-arm (fluoroscopy) and/or a portable x-ray machine during the reduction procedure. At his/her discretion, the orthopedic resident may use either of these modalities in both the ultrasound and control group as per standard of care in the PED. The use of these modalities will be recorded.

After the reduction procedure in the ultrasound group and prior to reviewing the post reduction x-ray, the orthopedic resident will complete a brief questionnaire with the following questions.

For the experimental group:

- a. Rate the ease of fracture reduction from 1-5, (1=easy 5=Very difficult)
- b. Was ultrasound helpful in completing the fracture reduction? a) yes b) no c) uncertain
- c. Rate the ease of using ultrasonography on a 5 point scale (1- easy, 5=very difficult).

The control group will undergo fracture reduction without ultrasound guidance as per the current standard of care in the PED. After the reduction procedure in the control group, the orthopedic resident will complete a brief questionnaire with the following questions:

For the control group:

IRB #:

Version 1.2

- a. Rate the ease of fracture reduction from 1-5, (1=easy 5=very difficult)
- b. Do you think real-time imaging would have been helpful for this reduction?

After the reduction and casting is completed, patients in both groups will undergo a post-reduction x-ray. Based on the degree of displacement on the x-ray, the orthopedic surgeon will determine whether the patient needs a repeat reduction, as per routine standard of care. If a repeat reduction is required, the treating physician can choose to use ultrasound at his/her discretion. The angle of displacement will be measured on the post-reduction x-ray by an orthopedic surgeon. Additionally, the angle of displacement measured on the post-reduction ultrasound will be measured and compared to the angle of displacement on the post-reduction x-ray. An expert sonographer will review cases where the ultrasound and x-ray results do not correlate.

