### **IVb. Protection against risk**

In the unlikely event that a patient is unable to tolerate the ultrasound procedure, the ultrasound will be discontinued immediately and the patient will be removed from the study. There are no infectious risks from the use of ultrasound in this study; open fractures are excluded, and the US machine will be cleaned per routine procedure after each use.

The risk of patient confidentiality being violated in this study is minimal due to the numerous safeguards that have been implemented (see section IVa).

---

 Simanovsky et al. Sonographic detection of radiographically occult fractures in paediatric ankle injuries. Pediatr Radiol 2005; 35(11):1062-5.

IRB #:

Version 1.2

**V. INVESTIGATOR QUALIFICATIONS AND EXPERIENCE** – see attached CV**VI. SUBJECT IDENTIFICATION, RECRUITMENT AND CONSENT/ASSENT****VIa. Consent and Procedure Timeline / Process**

The PEM attending, fellow or orthopedic resident caring for the patient will determine if the patient is eligible for inclusion in this study. If the patient is eligible and does not meet any of the exclusion criteria, the patient will be asked to participate (see written consent and child assent documents). The patient will be randomized to one arm of the study only after obtaining written consent from the patient  $\geq$  18 years of age or the parent/guardian of a minor and assent if the child is  $\geq$  7 years.

The experimental group will have an ultrasound performed prior to, during and after forearm fracture reduction. The ultrasound procedure involves placing ultrasound gel over the fracture site. The ultrasound probe is then placed in contact with the gel but not with the underlying skin. Images of the bony cortex are obtained in both longitudinal and transverse orientations and recorded on the ultrasound hard drive. After completion of the post-reduction ultrasound, the ultrasound gel will be removed, and the patient will undergo routine casting/splinting and post-reduction x-ray as per the Pediatric ED standard of care. The control group will undergo the standard of care fracture reduction with post-procedure x-ray images.

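### Patients who find the ultrasound uncomfortable are removed after randomisation, in practice from one arm only, and nothing keeps them in an as-randomised analysis

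*Combined protocol and SAP*

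**What the plan says.** Section IIc (Vulnerable subjects) covers a patient who expresses any discomfort from the ultrasound examination: "the procedure will be immediately discontinued and the patient will be removed from the study". Section IVb (Protection against risk) gives a parallel rule with a different trigger. The trigger there reads "In the unlikely event that a patient is unable to tolerate the ultrasound procedure", and the consequence that follows from it is that "the ultrasound will be discontinued immediately and the patient will be removed from the study".

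Sections IIIa and VIa place randomisation after consent and before any study ultrasound. Section VIa then says: "The experimental group will have an ultrasound performed prior to, during and after forearm fracture reduction". Under section IIIa, controls have their initial reduction without ultrasound. The one exception comes later: "If a repeat reduction is required, the treating physician can choose to use ultrasound at his/her discretion".

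Section IIId (Number of Subjects) names a chi-square test, confidence intervals and regression. It defines no analysis population and gives no rule for removed patients. It adds: "The statistical approaches will be further developed with the assistance of the statistician in the orthopaedic surgery department following data collection and study approval".

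**The concern.** Each of the two rules names two acts: stopping the ultrasound, and removing the patient from the study. The second is the statistical problem. It is a post-randomisation exclusion triggered by the experimental procedure, so a comparable control patient cannot be excluded in the same way before the outcome is decided. Discretionary ultrasound at a repeat reduction does not restore the balance, because by then the primary event in section Ib has already occurred.

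The effect depends on who is removed:

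- If discomfort marks harder fractures, likely failures leave the ultrasound arm while similar controls stay in, which favours ultrasound.
- If it marks easier cases, the bias runs against ultrasound.
- If it is unrelated to outcome, only a little power is lost.

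A link with difficulty is plausible but is inference. Section IIIa has scanning repeated until alignment is best, so a harder reduction may mean more scanning and more chance of triggering the rule. The arm is also known at the bedside when discomfort is judged; the only blinded role described, in section Ic, is the x-ray reader. Because section IIId leaves the statistical approach to be developed later, the handling of removed patients could be settled once outcomes are known.

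**Working it through.** **Inputs from section IIId (Number of Subjects).** Control rate 25% (5 of 20), ultrasound rate 6%, 56 per group, 80% power, alpha 0.05 (taken as two-sided), chi-square test. The 25% counts repeat reduction and/or operative management; it is used here as the repeat-reduction rate, as the plan's own calculation does.

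**The plan's figure.** With pooled variance and no continuity correction, the mean rate is (0.25 + 0.06)/2 = 0.155 and

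n = [1.960·√(2·0.155·0.845) + 0.842·√(0.25·0.75 + 0.06·0.94)]² / 0.19² = 55.8, so 56 per group.

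The stated figure reproduces. Exact power of the uncorrected chi-square test at 56 per group is 0.827.

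**Assumptions.** The documents give no removal rate and no failure rate among removed patients. Let r be the share of the ultrasound arm removed and f the share of those who would have failed.

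**Bias with no true effect (25% in both arms).** The failure rate among retained ultrasound patients is q = (0.25 − r·f)/(1 − r). For example, r = 5% and f = 100% gives (0.25 − 0.05)/0.95 = 0.2105, a shift of 0.25 − 0.2105 = 3.9 points. False-positive rates come from exact binomial enumeration of the uncorrected two-sided chi-square test with 56 controls. With no removals the rate is 0.051.

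| r (retained n) | f | shift favouring ultrasound | false-positive rate |
|---|---|---|---|
| 2% (55) | 50% | 0.5 points | 0.051 |
| 2% (55) | 100% | 1.5 points | 0.055 |
| 5% (53) | 50% | 1.3 points | 0.054 |
| 5% (53) | 80% | 2.9 points | 0.067 |
| 5% (53) | 100% | 3.9 points | 0.081 |
| 10% (50) | 50% | 2.8 points | 0.062 |
| 10% (50) | 80% | 6.1 points | 0.115 |
| 10% (50) | 100% (extreme) | 8.3 points | 0.180 |

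The planned difference is 19 points. If only 10% of removed patients would have failed, the shift runs the other way: 0.3, 0.8 and 1.7 points against ultrasound at r = 2%, 5% and 10%.

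**Worked trial results** (uncorrected chi-square, controls 14/56):

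| Situation | All randomised | After removals |
|---|---|---|
| Borderline, two failures removed | 7/56, p = 0.090 | 5/54, p = 0.029 |
| Borderline, two non-failures removed | 6/56, p = 0.048 | 6/54, p = 0.059 |
| Near planned rates, two failures removed | 5/56, p = 0.024 | 3/54, p = 0.005 |

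Two patients can move a borderline result across 0.05 in either direction. Near the planned rates the result stays significant.

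**Removal unrelated to outcome.** Exact power at 25% against 6% falls from 0.827 to 0.820, 0.819 and 0.798 at 2%, 5% and 10% removed.

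**The case against.** The strongest reply is that sections IIc and IVb are subject-protection text. Removal may mean only that study procedures stop, and neither section says that the routine x-ray or repeat-reduction result is discarded. That reading is possible, but no section states it, and both rules already say separately that the ultrasound stops. The ambiguity itself has to be settled before enrolment.

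The second reply is rarity, and much of it stands. Section IVb calls the event unlikely and section IIc calls ultrasound painless. Section IIIa keeps the probe on gel rather than skin, and says "All patients will undergo procedural sedation and/or pain management for closed reduction as per standard of care in the PED". Sections Ia and IVa cite earlier reports of no worsening of pain. At 2% removed the false-positive rate barely moves, even if every removed patient would have failed. The larger figures need 5% to 10% removal with a high failure share, which nothing in the documents supports, and the borderline example uses 7/56 (12.5%), about twice the planned 6%. Still, the word unlikely is attached only to inability to tolerate, not to the wider trigger of any discomfort. Rarity limits the size of the bias; it gives no reason to exclude these patients.

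Third, section IIIb names adequate angulation on x-ray as the primary endpoint, whereas section Ib names repeat reduction. The magnitudes above apply to repeat reduction. The one-arm exclusion applies to either outcome at the first post-reduction x-ray.

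**Conclusion.** The concern holds and should be fixed. Followed as written, the plan excludes patients after randomisation, from the ultrasound arm only until the primary outcome is decided, with no as-randomised analysis to protect the comparison. That much rests on the text alone.

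The direction and size of any bias are unknown. At the low removal rates the protocol expects, the effect is small: at most 1.5 points and a false-positive rate of 0.055 at 2% removed. It matters if removals reach 5% to 10% and are strongly related to failure, or if the result is borderline. A result at the planned rates would survive two removed failures. The removal rates and the failure shares among removed patients are assumptions throughout.

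**What to change.** Leave the instruction to stop the ultrasound unchanged, and make these changes before enrolment:

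1. In sections IIc and IVb, replace removal from the study with a statement that the patient stays in the assigned arm and that post-reduction x-ray, repeat reduction and operative repair are still collected unless consent is withdrawn.
2. Reconcile the two triggers (any discomfort; unable to tolerate).
3. In section IIId (Number of Subjects), state that all randomised patients are analysed by assigned group, and that the number of ultrasound discontinuations and the reasons will be reported.

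**Cost.** Wording in three sections, plus the consent and assent forms (section VIe; not available for this review) if they repeat the removal wording. No new procedure is needed: section IIIa says that "patients in both groups will undergo a post-reduction x-ray", and the repeat-reduction decision is routine care. Operative repair is already a secondary outcome in section Ib.

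**Downside.** Retaining these patients dilutes the effect. If those who stop ultrasound fail at 25% and the others at 6%, the ultrasound-arm rate is 0.06·(1 − r) + 0.25·r, which is 6.4%, 7.0% and 7.9% at r = 2%, 5% and 10%. Exact power with 56 per arm then falls from 0.827 to 0.805, 0.771 and 0.710. The loss is small if the event is as rare as the protocol expects.
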